## 8.2.5.1 Guidelines for management of elevated liver enzymes

Participants with signs or symptoms consistent with liver injury (eg, nausea, vomiting, anorexia, fatigue, right upper abdominal pain or discomfort) should undergo immediate testing of ALT, AST, gamma-glutamyl transferase, bilirubin, alkaline phosphatase, prothrombin time, and international normalized ratio.

In the absence of clinical symptoms, participants with ALT or AST  $>3 \times$  ULN (if normal at Baseline) or >2-fold change (if abnormal at Baseline) should be retested within 48 to 72 hours for the usual serum measurements (ALT, AST, alkaline phosphatase, and bilirubin) to confirm the abnormalities and to determine if the associated values are increasing or decreasing. There should also be an inquiry about symptoms at the time of follow-up.

If the above abnormalities are confirmed:

- Repeat liver enzyme and serum bilirubin tests 2 or 3 times weekly. The frequency of retesting can decrease to once a week or less if abnormalities stabilize or the study drug has been discontinued and the participant is asymptomatic;
- Obtain a more detailed history of symptoms and prior or concurrent diseases;
- Obtain a history of concomitant drug use (including nonprescription medications and herbal and dietary supplement preparations), alcohol use, recreational drug use, and special diet;

- Rule out acute viral hepatitis types A, B, C, D, and E; autoimmune or alcoholic hepatitis; nonalcoholic steatohepatitis; hypoxic/ischemic hepatopathy; and biliary tract disease;
- Obtain a history of exposure to environmental chemical agents;
- Obtain additional tests to evaluate liver function, as appropriate (eg, international normalized ratio, direct bilirubin); and
- Consider gastroenterology or hepatology consultations.

Study drug discontinuation should occur if:

- ALT or AST >8 × ULN;
- ALT or AST >5 × ULN for more than 2 weeks;
- ALT or AST >3 × ULN and total bilirubin >2 × ULN or international normalized ratio >1.5;
   or
- ALT or AST  $>3 \times$  ULN with the appearance of fatigue, nausea, vomiting, right upper quadrant pain or tenderness, fever, rash, and/or eosinophilia (>5%).

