#### 4.2 Exclusion Criteria

Participants who meet any of the following criteria will be excluded from participation in the study:

- 1. Have current or any previous history of New York Heart Association class III or IV HF or left ventricular ejection fraction <30%;
- 2. Have been hospitalized for HF within 5 years prior to Screening (Visit 1);
- 3. Have had any of the following clinical events within 3 months prior to Screening (Visit 1):
  - o Non-fatal MI;
  - Non-fatal stroke;
  - o Non-elective coronary revascularization; and/or
  - O Hospitalization for unstable angina and/or chest pain.
- 4. Have uncontrolled severe hypertension, defined as either systolic blood pressure ≥160 mmHg or diastolic blood pressure ≥100 mmHg prior to Randomization (Visit 2) taken as the average of triplicate measurements. One triplicate retest will be allowed during the same visit, at which point if the retest result is no longer exclusionary, the participant may be randomized;
- 5. Have a formal diagnosis of homozygous FH;
- 6. Have active liver disease, defined as any known current infectious, neoplastic, or metabolic pathology of the liver; unexplained elevations in alanine aminotransferase (ALT) or aspartate aminotransferase (AST) >3 × upper limit of normal (ULN); or total bilirubin >2 × ULN at Screening (Visit 1);
  - Note: An abnormal ALT, AST, or total bilirubin must be confirmed by a repeat abnormal measurement at least 1 week apart.
- 7. Have HbA1c ≥10.0% (≥0.100 hemoglobin fraction) or a fasting glucose ≥270 mg/dL (≥15.0 mmol/L) at Screening (Visit 1);
- 8. Have thyroid-stimulating hormone  $\geq 1.5 \times ULN$  at Screening (Visit 1);
- 9. Have creatine kinase (CK)  $>3 \times$  ULN at Screening (Visit 1);
- 10. Have a history of a malignancy that required surgery (excluding local and wide local excision), radiation therapy, and/or systemic therapy during the 3 years prior to Randomization (Visit 2);
- 11. Have a known history of alcohol and/or drug abuse within 5 years prior to Randomization (Visit 2);

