#### 4.3 Withdrawal Criteria

Participation of a participant in this clinical study will be discontinued for any of the following reasons:

- Withdrawal of consent; or
- Termination of the study by the Sponsor or the regulatory authority.

Study drug treatment may be discontinued either permanently or temporarily (although the participant should be encouraged to remain in the study and to follow-up for study visits) for any of the following reasons:

- Occurrence of any medical condition or circumstance that exposes the participant to substantial risk and/or does not allow the participant to adhere to the requirements of the protocol;
- Any serious AE (SAE), clinically significant AE, severe laboratory abnormality, intercurrent illness, or other medical condition which indicates to the Investigator that continued participation is not in the best interest of the participant;
- Pregnancy (permanent discontinuation of study drug);

- Requirement of prohibited concomitant medication; or
- Participant failure to comply with protocol requirements or study-related procedures.

Participants are free to withdraw consent from the study (which means permanent discontinuation of study drug and all follow-up assessments) at any time without prejudice. Note that discontinuation of study drug in and of itself is **not** considered withdrawal of consent.

An excessive rate of withdrawals (either discontinuation of study drug or study withdrawal) can render the study non-interpretable. Therefore, unnecessary withdrawal of participants should be avoided, and all efforts should be taken to motivate participants to comply with all of the study-specific procedures and to continue follow-up until the end of the study to detect the occurrence of CV events and assess vital status.

Every attempt should be made to keep participants on study drug throughout the duration of the study. Before permanently discontinuing study drug (either participant- or Investigator-initiated), an interruption should be considered. Participants who temporarily discontinue study drug for any reason should restart as soon as it is medically justified in the opinion of the Investigator. In addition, participants should not be withdrawn from the study drug or from the study after experiencing a potential CV event.

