## 8.2.5.2 Guidelines for monitoring and management of CK

If at any time after Randomization (Visit 2) a participant experiences a CK elevation  $>5 \times ULN$ , the participant will undergo a repeat confirmatory assessment as soon as is reasonably possible, preferably within 3 to 7 days of the laboratory result becoming available.

A repeat CK assessment will include query for related symptoms.

If the repeat CK assessment confirms an unexplained (ie, not associated with recent trauma or physically strenuous activity) CK abnormality >5 × ULN and the participant is asymptomatic, he/she should receive further assessment and investigation into the cause, assessment of whether there is renal injury, and measurement of CK approximately weekly, or more frequently if clinically indicated, until resolution. If CK levels continue to rise, the study drug should be discontinued.

If the participant experiences a CK elevation  $>5 \times$  ULN and is symptomatic, the following should be completed:

- Interruption of study drug;
- Clarification of the nature, duration, and intensity of muscle symptoms;
- Review of possible predisposing factors, such as unaccustomed exercise, heavy alcohol intake, and viral illness (consider performing serology);
- Evaluation for additional diagnoses or other conditions which can cause myopathy, including muscle tenderness (by physical examination), weakness, rash, measurement of serum creatinine, and/or urine dipstick analysis with microscopy if indicated;
- Measurement of clinical chemistries to assess the possibility of lactic acidosis; and
- Follow-up of symptoms and CK until the abnormality has resolved.

If, based on the above evaluation, an alternative explanation is suspected, consideration can be given to resuming study drug once CK returns to Baseline levels.

If no alternative explanation exists, consideration should be given to withdrawing the participant from study drug treatment.

If the repeat CK assessment confirms an unexplained (ie, not associated with recent trauma or physically strenuous activity)  $CK > 10 \times ULN$ , the participant should be withdrawn and given no further doses of study drug, even in the absence of symptoms. The signs and symptoms and laboratory assessments as outlined above should also be evaluated. The participant should continue being followed in the study for safety.

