## 8.2.5.4 Guidelines for monitoring and management of significant changes in renal function

If at any time after Randomization (Visit 2) a participant experiences ANY of the following, the participant will undergo a repeat confirmatory assessment as soon as is reasonably possible, preferably within 3 to 7 days of the laboratory result becoming available:

- A >25% decrease in eGFR from Baseline, calculated using the Chronic Kidney Disease Epidemiology Collaboration equation;
- An eGFR <30 mL/min/1.73 m^2, calculated using the Chronic Kidney Disease Epidemiology Collaboration equation; and/or
- An increase in serum creatinine of  $\geq 0.3$  mg/dL ( $\geq 26.5$  µmol/L) from Baseline.

In consultation with the Medical Monitor and/or nephrologist, if no alternative etiology is determined, the study drug should be discontinued if participants experience an unexplained, confirmed increase in serum creatinine of  $\geq 0.3$  mg/dL ( $\geq 26.5$  µmol/L) from Baseline or an unexplained, confirmed  $\geq 25\%$  decrease in eGFR from Baseline.

If any of these individual laboratory parameters are confirmed, such events of decline in renal function should be recorded as an ESI.

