#### 9.2 Statistical Methods

An SAP will be finalized before database lock. Any changes to the methods described in the SAP will be described and justified as needed in the final Clinical Study Report. All study-collected data will be summarized by treatment group using descriptive statistics, graphs, and/or raw data listings. Descriptive statistics for continuous variables will include number of participants, mean, standard deviation, median, minimum, and maximum values. Analyses of categorical variables will include frequency and percentage.

Unless otherwise stated, Baseline values will be the last non-missing measurements taken prior to the participant receiving study drug.

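### With Baseline ALT/AST above 2.5 × ULN, an asymptomatic value above 5 × ULN can miss the timed retest that the two-week stopping rule needs

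*Protocol*

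**What the plan says.** Protocol 8.2.5.1 gives asymptomatic participants one of two ALT/AST retest triggers, depending on Baseline. With a normal Baseline it is a value above 3 × ULN. With an abnormal Baseline the text reads "or >2-fold change (if abnormal at Baseline) should be retested within 48 to 72 hours", and no multiple of ULN is attached to that branch. Only if the retest confirms the abnormality does the next instruction apply: "Repeat liver enzyme and serum bilirubin tests 2 or 3 times weekly".

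The discontinuation list in the same section does not depend on Baseline. It includes a single value above 8 × ULN, "ALT or AST >5 × ULN for more than 2 weeks", and values above 3 × ULN combined with raised bilirubin or INR, with symptoms, or with eosinophilia.

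On who can enter with a raised Baseline, Protocol 4.2, criterion 6, excludes active liver disease. That covers known current infectious, neoplastic or metabolic liver pathology at any enzyme level. It also covers "unexplained elevations in alanine aminotransferase (ALT) or aspartate aminotransferase (AST) >3 × upper limit of normal (ULN") at Screening, confirmed by a repeat. Under Protocol 9.2, "Baseline values will be the last non-missing measurements taken prior to the participant receiving study drug", so Baseline is normally the Day 1 sample and not the Screening sample used for eligibility.

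**The concern.** A rule about persistence needs at least two values, suitably spaced. The guideline provides those values through the retest and the serial testing that follows it. For an abnormal Baseline, however, that route opens only on a relative change, while the stopping rule is absolute. Where twice Baseline lies above 5 × ULN, a participant can be in the range the stopping rule addresses without the guideline asking for a second sample.

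The result is an odd ordering. A participant with normal Baseline and 3.1 × ULN on treatment gets a retest within three days. One with Baseline 2.8 and 5.4 × ULN gets no timed retest, and the documents give no reason for the difference.

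The other laboratory guidelines avoid this. For CK above 5 × ULN, whatever the Baseline, "the participant will undergo a repeat confirmatory assessment as soon as is reasonably possible" (Protocol 8.2.5.2). The renal guideline combines Baseline-relative triggers with an absolute eGFR limit: "If at any time after Randomization (Visit 2) a participant experiences ANY of the following" (Protocol 8.2.5.4).

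At stake is the timing of a safety decision in a small group. No endpoint, error rate or efficacy estimate is involved.

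**Working it through.** The plan states no figure to reproduce; the check is threshold and calendar arithmetic.

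**Inputs**
- Retest trigger with abnormal Baseline *B* (in × ULN): value above 2*B*, taking the 2-fold wording as a ratio to Baseline (8.2.5.1).
- Stopping thresholds: above 5 × ULN for more than 14 days; above 8 × ULN on one value (8.2.5.1).
- Highest unexplained Screening value admitted: 3 × ULN (4.2, criterion 6).
- Scheduled post-dose chemistry: Days 30, 84, 180, 270 and 365, with windows of ±3 days at Day 30 and ±7 days afterwards (Appendix A).

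**Step 1: where the gap opens.** A value above 5 can fail to exceed 2*B* only if 2*B* > 5, that is *B* > 2.5.

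**Step 2: size of the band.** Width = 2*B* − 5.

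| Baseline (× ULN) | Retest fires above | Uncovered values | Width |
|---|---|---|---|
| 2.5 | 5.0 | none | 0 |
| 2.6 | 5.2 | >5 to 5.2 | 0.2 |
| 2.8 | 5.6 | >5 to 5.6 | 0.6 |
| 3.0 | 6.0 | >5 to 6.0 | 1.0 |

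Example: Baseline 2.8, on treatment 5.4. The ratio is 5.4/2.8 = 1.93, so there is no trigger.

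**Step 3: 3 × ULN is not a hard ceiling for Baseline.** A Day 1 value above Screening, or an elevation with a known non-hepatic cause, could exceed it. At Baseline 3.5 the band would run to 7.0, and at 4.0 to 8.0, where the single-value rule takes over.

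**Step 4: what the missed trigger costs.** After a confirmed trigger, 2 to 3 tests a week give 2 × 2 = 4 to 3 × 2 = 6 values in two weeks. In the uncovered band the guideline asks for none.

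**Step 5: time to the next scheduled chemistry.**

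| Interval | Nominal days | With windows |
|---|---|---|
| Day 30 to 84 | 54 | 44 to 64 |
| Day 84 to 180 | 96 | 82 to 110 |
| Day 180 to 270 | 90 | 76 to 104 |
| Day 270 to 365 | 95 | 81 to 109 |

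Against the 14-day criterion, the nominal gaps are 54/14 = 3.9 to 96/14 = 6.9 times as long; with windows, 44/14 = 3.1 to 110/14 = 7.9 times. SAP 3.1.2, Table 3, shows an extra Day 14 visit in Japan. Whether chemistry is drawn then is not stated. If it is, the next visit is nominally 30 − 14 = 16 days later, and the later gaps are unchanged.

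**Step 6: sensitivity to wording.** If the 2-fold change meant the increment, the trigger would be a value above 3*B*. The gap would then open at *B* = 5/3 = 1.67, and at *B* = 3.0 the trigger (9.0) would leave the whole range from above 5 to 8 × ULN uncovered. The ratio reading is the usual one and is used for the conclusion.

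**The case against.** The strongest reply is that the group is narrow and follow-up already exists.

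- **Eligibility.** Criterion 6 removes known liver pathology at any enzyme level, and criterion 17 lets the Investigator exclude anyone at increased risk. What remains is unexplained Screening values up to 3 × ULN, non-hepatic causes, and Day 1 values above Screening. This stands: the affected group is probably small and could be empty.
- **Scope.** A reader might infer that any abnormal Baseline lacks protection above 5 × ULN. The text does not support that. At Baseline 2.5 × ULN or below, every value above 5 × ULN exceeds twice Baseline and triggers the retest. Symptomatic participants are tested at once, and values above 8 × ULN stop drug without a repeat.
- **Backstops.** A reader might also infer that such a value goes unexamined for two to three months. The text does not support that either. Protocol 8.2 has clinically significant laboratory values followed with repeat tests. Section 8.8.4 makes the Investigator judge change from Baseline and flags critical values at Laboratory Manual limits not available here. Section 4.3 allows discontinuation for "severe laboratory abnormality, intercurrent illness, or other medical condition which indicates to the Investigator" that continuing is not in the participant's interest. ALT/AST above 3 × ULN is an event of special interest, reviewed by the DSMB about every six months. An Investigator applying the two-week rule would have to repeat the test. The 54 to 96 days is therefore a worst case. What survives is that none of these provisions sets a retest time.
- **Precedents.** The CK and renal guidelines contain no two-week persistence rule, so they are not exact parallels. They show only that the protocol uses absolute limits elsewhere.

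A Baseline-relative trigger is itself a reasonable choice; the point concerns only the missing upper limit.

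**Conclusion.** The point holds in a limited form. For an asymptomatic participant with Baseline ALT or AST above 2.5 × ULN, the guideline can leave a value above 5 × ULN without a timed retest, although its own stopping rule needs one. The band is 0 to 1.0 × ULN wide for Baselines from 2.5 to 3.0 × ULN, and wider only if Baseline exceeds 3 × ULN. The conclusion assumes that the 2-fold wording means more than twice Baseline and that the Laboratory Manual sets no retest interval of its own. The number of participants affected cannot be derived from the documents. Severity is low: this is a cheap improvement to a safety guideline, not a defect in the trial's design or analysis.

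**What to change.** In Protocol 8.2.5.1, reword the asymptomatic trigger as: above 3 × ULN (if normal at Baseline); or more than twice Baseline or above 5 × ULN, whichever is lower (if abnormal at Baseline). The confirmation and serial-testing steps then follow as written, and the ratio reading is fixed explicitly.

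On that reading nothing changes for Baselines up to 2.5 × ULN. Above that, the retest fires at a smaller rise: 5/2.8 = 1.79-fold at Baseline 2.8 and 5/3.0 = 1.67-fold at Baseline 3.0. The cost is one clause and a few extra retests, confined to participants with Baseline above 2.5 × ULN. Efficacy endpoints and analyses are untouched.

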## 8.2.5.2 Guidelines for monitoring and management of CK

If at any time after Randomization (Visit 2) a participant experiences a CK elevation  $>5 \times ULN$ , the participant will undergo a repeat confirmatory assessment as soon as is reasonably possible, preferably within 3 to 7 days of the laboratory result becoming available.

A repeat CK assessment will include query for related symptoms.

If the repeat CK assessment confirms an unexplained (ie, not associated with recent trauma or physically strenuous activity) CK abnormality >5 × ULN and the participant is asymptomatic, he/she should receive further assessment and investigation into the cause, assessment of whether there is renal injury, and measurement of CK approximately weekly, or more frequently if clinically indicated, until resolution. If CK levels continue to rise, the study drug should be discontinued.

If the participant experiences a CK elevation  $>5 \times$  ULN and is symptomatic, the following should be completed:

- Interruption of study drug;
- Clarification of the nature, duration, and intensity of muscle symptoms;
- Review of possible predisposing factors, such as unaccustomed exercise, heavy alcohol intake, and viral illness (consider performing serology);
- Evaluation for additional diagnoses or other conditions which can cause myopathy, including muscle tenderness (by physical examination), weakness, rash, measurement of serum creatinine, and/or urine dipstick analysis with microscopy if indicated;
- Measurement of clinical chemistries to assess the possibility of lactic acidosis; and
- Follow-up of symptoms and CK until the abnormality has resolved.

If, based on the above evaluation, an alternative explanation is suspected, consideration can be given to resuming study drug once CK returns to Baseline levels.

If no alternative explanation exists, consideration should be given to withdrawing the participant from study drug treatment.

If the repeat CK assessment confirms an unexplained (ie, not associated with recent trauma or physically strenuous activity)  $CK > 10 \times ULN$ , the participant should be withdrawn and given no further doses of study drug, even in the absence of symptoms. The signs and symptoms and laboratory assessments as outlined above should also be evaluated. The participant should continue being followed in the study for safety.

Any event of rhabdomyolysis, regardless of CK level, should lead to study drug interruption or discontinuation until the contribution of obicetrapib has been excluded.

## 8.2.5.3 Guidelines for monitoring and management of NODM

Diabetes mellitus may be newly diagnosed during the study as described in Section 8.2.5. If a participant is newly diagnosed with diabetes mellitus during the course of the study, the Investigator will recommend referral for initial diabetes education and management by an appropriate healthcare provider (eg, diabetologist, endocrinologist, or primary care provider). Interventions for management may include diet and lifestyle counseling, self-monitoring of blood glucose, oral glucose-lowering medications, injectable medications, or insulin as deemed necessary by the treating physician based on the level of hyperglycemia and relevant symptoms.

## 8.2.5.4 Guidelines for monitoring and management of significant changes in renal function

If at any time after Randomization (Visit 2) a participant experiences ANY of the following, the participant will undergo a repeat confirmatory assessment as soon as is reasonably possible, preferably within 3 to 7 days of the laboratory result becoming available:

- A >25% decrease in eGFR from Baseline, calculated using the Chronic Kidney Disease Epidemiology Collaboration equation;
- An eGFR <30 mL/min/1.73 m^2, calculated using the Chronic Kidney Disease Epidemiology Collaboration equation; and/or
- An increase in serum creatinine of  $\geq 0.3$  mg/dL ( $\geq 26.5$  µmol/L) from Baseline.

In consultation with the Medical Monitor and/or nephrologist, if no alternative etiology is determined, the study drug should be discontinued if participants experience an unexplained, confirmed increase in serum creatinine of  $\geq 0.3$  mg/dL ( $\geq 26.5$  µmol/L) from Baseline or an unexplained, confirmed  $\geq 25\%$  decrease in eGFR from Baseline.

If any of these individual laboratory parameters are confirmed, such events of decline in renal function should be recorded as an ESI.

# 8.2.5.5 Guidelines for monitoring and management of changes to antihypertensive medication(s)

Any changes to antihypertensive medication(s) due to changes in blood pressure in those participants receiving antihypertensive medication(s) treatment at Baseline will be assessed by the Investigator, primary care physician, or other appropriate health care provider to assess for etiologies of blood pressure change, to confirm clinical safety of the participant, to assess the need for any AE or SAE reporting, and to arrange for appropriate medical follow-up.

